3 OBJECTIVES AND ENDPOINTS

OBJECTIVES	ENDPOINTS
Primary	
To test the effectiveness of two behavioral nudges, one based on peer behavior and one based on best practice guidelines, in reducing the share of discharge opioid prescriptions above procedure-specific prescribing guidelines	Share of discharge opioid prescriptions above prescribing guidelines
Secondary	
To test the effectiveness of two behavioral nudges, one based on peer behavior and one based on best practice guidelines, in reducing the morphine milligram equivalent quantities and days' supply prescribed at discharge	Morphine milligram equivalents (MMEs) prescribed at discharge, days' supply of opioids prescribed at discharge
To test the effectiveness of two behavioral nudges, one based on peer behavior and one	Share of discharges where any opioid was prescribed

OBJECTIVES	ENDPOINTS
based on best practice guidelines, in reducing the share of discharges with any opioids prescribed	
To test the long-term effects on patients of two behavioral nudges, one based on peer behavior and one based on best practice guidelines	Share of patients on opioids for greater than 3 months post-discharge
To test the persistence of the effectiveness of two behavioral nudges, one based on peer behavior and one based on best practice guidelines, in reducing the share of discharge opioid prescriptions above procedure-specific prescribing guidelines	Share of discharge opioid prescriptions above prescribing guidelines in the 12 months after the nudges stop being delivered
To test the safety of two behavioral nudges, one based on peer behavior and one based on best practice guidelines	Number of 30-day all-cause emergency department visits, number of 30-day all-cause hospitalizations

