8.2 SAFETY AND OTHER ASSESSMENTS

All safety assessments will be conducted using data collected from the Sutter Health electronic health record. Data collected will include:

- Dates and associated diagnoses of emergency department visits within 30 days of discharge
- Discharge opioid prescription refills

The study statistician will regularly create three reports for each outcome. Each report will feature a set of ratios indicating the relative frequency of adverse events in a different context. The reports will contain the numerator, denominator, and ratio, each individually reported. Reports will be produced at the end of each month of the trial, including through the 1-year post-intervention period. They will be presented and discussed at half-yearly DSMB meetings.

- Report 1: Adverse events per arm
 - a) Numerator: number of adverse events among intervention arm 1 (INT1) patients
 - Denominator: total number of INT1 patients meeting the inclusion criteria

- b) Numerator: number of adverse events among intervention arm 2 (INT2) patients
Denominator: total number of INT2 patients meeting the inclusion criteria
- c) Numerator: number of adverse events among the control patients
Denominator: total number of control patients meeting the inclusion criteria

- Report 2: Adverse events per arm among patients of surgeons who ever received a treatment email
 - a) Numerator: number of adverse events among patients whose surgeon ever received an INT1 email
Denominator: total number of patients whose surgeon ever received an INT1 email
 - b) Numerator: number of adverse events among patients whose surgeon ever received an INT2 email
Denominator: total number of patients whose surgeon ever received an INT2 email

Notes: Ever received an INT1/INT2 email means that the surgeon is included if they received an INT1/INT2 email in any month of the trial. We will also compare the report 2 ratios to the report 1 control ratio (item c above) for additional context.

- Report 3: Adverse events per arm among patients who were prescribed an opioid at discharge and whose surgeon who ever received a treatment email
 - a) Numerator: number of adverse events among patients prescribed opioids at discharge and whose surgeon ever received an INT1 email
Denominator: total number of patients prescribed opioids at discharge and whose surgeon ever received an INT1 email

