 - b) Numerator: number of adverse events among patients prescribed opioids at discharge and whose surgeon ever received a nINT2 email
Denominator: total number of patients prescribed opioids at discharge and whose surgeon ever received an INT2 email
 - c) Numerator: number of adverse events among control patients prescribed opioids at discharge
Denominator: total number of control patients prescribed opioids at discharge

Notes: Ever received an INT1/INT2 email means that the surgeon is included if they received an INT1/INT2 email in any month of the trial.

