9.4.2 ANALYSIS OF THE PRIMARY AND SECONDARY EFFICACY ENDPOINTS

Our primary outcome is the share of discharge prescriptions that were above the guideline for the respective procedure (see above for how guidelines were identified). Prescribing above guidelines is the outcome to which both nudges are linked (even though the descriptive norm nudge does not explicitly refer to guidelines) and thus a key measure of whether clinician behavior responds to the nudges. We define a prescription as being above guidelines if the morphine milligram equivalent (MME) quantity of opioids prescribed is above the ceiling for the procedure-specific guideline (guidelines range from zero to a ceiling). If no opioid is prescribed at discharge, we will code this as within guideline.

We will also analyze the following secondary outcomes to further understand the effects of the intervention.

- MMEs prescribed at discharge
- Days' supply of opioids prescribed at discharge
- Share of discharges where any opioid was prescribed
- Share of patients on opioids for greater than three months post-discharge
- Number of 30-day all-cause emergency department visits
- Number of 30-day all-cause hospitalizations
- Share of discharge opioid prescriptions above prescribing guidelines in the 12 months after the nudges end

Primary analysis

We will analyze outcomes at the level of the discharge using a four-level hierarchical linear model (HLM),[42] thus capturing the clustering inherent in the study design and data generating process. We will analyze outcomes at the patient level, and patients are nested within surgeons, who are nested within specialties, which are nested within hospitals. Both primary and secondary outcomes will follow this modeling structure. To improve the precision of our estimates, we will also include a set of observable patient covariates (X), surgeon covariates (Z), specialty covariates (U), and hospital covariates (W). For patient i , treated by surgeon p , in specialty s , at hospital h , we consider the following HLM formulation for continuous outcomes Y_{ipsh} :

$$Y_{ipsh} = \beta_0 + \beta_1 ARM1_{sh} + \beta_2 ARM2_{sh} + \gamma_{1h} ARM1_{sh} + \gamma_{2h} ARM2_{sh} + \omega_1 X_{ipsh} + \omega_2 Z_{psh} + \omega_3 U_{sh} + \omega_4 W_h + \gamma_h + \eta_{sh} + \varphi_{psh} + \varepsilon_{ipsh} \quad (1)$$

$ARM1_{sh}$ and $ARM2_{sh}$ are indicator variables for whether specialty s , at hospital h were assigned to intervention arm one or two respectively.

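### Safety Report 3 compares arms on emergency visits only among patients sent home with an opioid, a status the nudges aim to change, so it can miss harm or show a false difference.

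*Combined protocol and SAP*

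**What the plan says.** Section 8.2 lists two safety outcomes, emergency department visits within 30 days of discharge and refills of the discharge opioid. It plans three reports for each, produced monthly and discussed at half-yearly DSMB meetings. Section 9.4.3 refers to Section 8.2 for the safety analysis.

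- Report 1 counts events per arm. Its denominators are of the form "total number of INT1 patients meeting the inclusion criteria".
- Report 2 covers patients of surgeons who were ever emailed. It names no opioid condition and has no control row of its own; it is set beside the Report 1 control ratio for context.
- Report 3 is headed "Adverse events per arm among patients who were prescribed an opioid at discharge". Its two nudge rows also require a surgeon who was ever emailed. Its control row (item c) has as numerator the "number of adverse events among control patients prescribed opioids at discharge", with a matching denominator and no email condition. Its note carries no caution about comparing the rows.

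Section 3 lists a secondary objective of testing the nudges "in reducing the share of discharges with any opioids prescribed". In Section 9.4.2, "guidelines range from zero to a ceiling", and "If no opioid is prescribed at discharge, we will code this as within guideline". Sending a patient home without an opioid is therefore a compliant response to either nudge.

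**The concern.** The Report 3 condition is fixed only when the discharge order is written, after randomisation, and it is one of the outcomes the trial hopes to move. If the nudges lower the any-opioid share, some nudge-arm patients who would have received an opioid under usual care go home without one. Their events leave rows a and b. Patients like them in the control arm still receive an opioid and stay in row c. The condition is worded alike in every arm but selects different kinds of patient.

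Two errors can follow for emergency visits. Harm caused by withholding an opioid falls on exactly the patients missing from the nudge rows, so Report 3 cannot show it. And with no effect on visits at all, the ratio still moves if the patients who leave differ in risk from those who stay. It looks like harm if the leavers are at lower risk, and like benefit if they are at higher risk. The DSMB reads these reports and may recommend stopping the intervention (Section 7.1).

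**Working it through.** No figure in the plan depends on this point, so there is none to reproduce. The calculation below is illustrative. It leaves out the ever-emailed condition in order to isolate the opioid condition.

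**Inputs**
- p, the control any-opioid share: not in the documents. Assumed 80%, with 70% and 90% as a range.
- d, the fall in that share under a nudge: not in the documents. Taken as 0, 2, 5 and 13.9 points. The largest applies the upper minimum detectable effect in Section 9.2 to a binary outcome: 0.347 × √(0.8 × 0.2) = 0.139. That effect size was derived for medication dose, so it serves here only as a large case.
- k, the event risk of the patients moved to no opioid, relative to patients who receive an opioid in either arm: assumed 0.5 or 1.5.
- No patient receives an opioid because of a nudge (assumed).

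**No true effect on visits.** With risk r in patients who receive an opioid in either arm:
- Report 3 nudge risk = r
- Report 3 control risk = [(p − d)r + d·k·r] / p
- Report 3 risk ratio = 1 / [1 − (d/p)(1 − k)]

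Example with d = 0.05: d/p = 0.0625. For k = 0.5 the ratio is 1/(1 − 0.03125) = 1.03. For k = 1.5 it is 1/(1 + 0.03125) = 0.97.

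**Harm confined to the moved patients.** Suppose all patients have the same baseline risk and losing the opioid doubles it. The all-patient risk ratio is then 1 + d, while Report 3 shows 1.00 because those patients are not in its nudge rows.

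Results at p = 80%:

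| Fall d | d/p: share of row c with no nudge counterpart | Report 3 ratio, no effect, k = 0.5 | Report 3 ratio, no effect, k = 1.5 | All-patient ratio if risk doubles | Report 3 ratio if risk doubles |
|---|---|---|---|---|---|
| 0 | 0% | 1.00 | 1.00 | 1.00 | 1.00 |
| 2 points | 2.5% | 1.01 | 0.99 | 1.02 | 1.00 |
| 5 points | 6.3% | 1.03 | 0.97 | 1.05 | 1.00 |
| 13.9 points | 17.4% | 1.10 | 0.92 | 1.14 | 1.00 |

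Varying p from 70% to 90% changes little. For k = 0.5 a 5-point fall gives 1.04 to 1.03 and a 13.9-point fall 1.11 to 1.08. For k = 1.5 they give 0.97 throughout and 0.91 to 0.93.

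**In absolute terms**, with a fall from 80% to 70% and assumed event rates:
- Harm only in the moved patients, 8% rising to 16%. All-patient rates are 8.0% in control and 0.7 × 8% + 0.1 × 16% + 0.2 × 8% = 8.8% under the nudge. Report 3 shows 8.0% in both.
- No effect, with moved patients at 3% and patients given an opioid in either arm at 8%. Report 3 shows (0.7 × 8% + 0.1 × 3%) / 0.8 = 7.4% in control and 8.0% under the nudge, a false excess of 0.6 points.

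**Is Report 1 a safeguard?** Its denominators are patients who meet the inclusion criteria. Section 5.1 writes those criteria for prescriptions, and one of them is that the prescription is for an oral opioid. Applied literally, Report 1 would also drop patients without an opioid. Section 9.4.2, which assigns a code to discharges with no opioid, points the other way. The two sections do not settle the matter.

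**The case against.** The strongest reply is that Report 3 is one of three views in the same package. Report 1 is meant to show events per arm without the opioid condition, and Report 2 names no such condition. If Report 1 held only patients with an opioid, items 1c and 3c would be nearly identical, so the layout itself suggests that Report 1 is wider. Sections 9.3 and 9.4.2 also put 30-day emergency visits and hospitalisations into the outcome model on the intention-to-treat set. A reader might infer that safety monitoring as a whole is blind to this harm; the documents do not support that. What remains is that the breadth of Report 1 must be inferred against Section 5.1, and the outcome model is not the monthly DSMB report.

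Numerators and denominators are reported separately, so subtraction recovers some of the missing patients. Report 2 minus Report 3 gives those without an opioid in the nudge arms, and item 1c minus item 3c gives those in control. This is true, but the nudge figures cover only ever-emailed surgeons and the control figures cover the whole arm, so they are not like for like.

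Three further stronger readings should be resisted:
- A reader might infer that control patients sent home without an opioid are counted. They are not, because item c applies the same condition. The asymmetry concerns only patients whose opioid status the nudge changes, a group that cannot be identified individually.
- A reader might take the Section 9.2 effect size as the expected fall in the any-opioid share. It is a detectable effect for dose. The emails are triggered by quantities above a ceiling, and a surgeon can comply by prescribing less without prescribing none. Small falls are quite possible, and the bias is then small.
- A reader might infer that Report 3 could trigger a stopping rule. The documents attach no test, threshold or rule to it.

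For refills, patients given an opioid are the natural denominator, although the selection still happens after randomisation.

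**Conclusion.** The concern holds for Report 3 and emergency visits. The report sets nudge rows against a control row within a group defined by a result the nudges aim to change, and it does so without a caution. Its direction of error is not known in advance, and it cannot show harm in patients moved to no opioid.

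The size depends on the fall in the any-opioid share and on how the moved patients differ in risk, and the documents give neither. In the illustration the false ratio ranges from about 1% either way for a 2-point fall to 1.10 or 0.92 for a 13.9-point fall, and it vanishes if the share does not fall. The problem is confined to Report 3 provided Report 1 counts discharges without an opioid, which the current text leaves open. It should be corrected because correction is cheap, but it does not threaten the primary analysis.

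The ever-emailed condition on rows a and b, absent from row c, is a separate imbalance and is not included in these figures.

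**What to change.** 1. State in Section 8.2 that Report 1 is the arm comparison for emergency visits, and that it counts all otherwise eligible discharges whether or not an opioid was prescribed. Reconcile Section 5.1 with Section 9.4.2 on this point.
2. For emergency visits, show two rows for each whole arm, without the ever-emailed condition: patients with a discharge opioid and patients without. The two rows then sum to Report 1, and events in patients sent home without an opioid become visible in every arm. The split rows are themselves descriptive; the comparison rests on their sum.
3. Keep the present Report 3 rows for refills. For emergency visits, label them descriptive and not an arm comparison.

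Optionally, add a subgroup fixed before discharge and applied alike in all arms, such as procedures whose any-opioid share in the baseline period (1 June 2020 to 18 October 2021, Section 9.4.4) reached a level set in advance. It would include some patients who would never have received an opioid, and if most procedures qualify it adds little to Report 1.

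The cost is a wording change, a small change to the monthly report code and a few extra rows. No new data are needed.

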8.3 ADVERSE EVENTS AND SERIOUS ADVERSE EVENTS

8.3.1 DEFINITION OF ADVERSE EVENTS (AE)

Adverse event means any untoward medical occurrence associated with the use of an intervention in humans, whether or not considered intervention-related (21 CFR 312.32 (a)).]

8.3.2 DEFINITION OF SERIOUS ADVERSE EVENTS (SAE)

An adverse event (AE) or suspected adverse reaction is considered “serious” if, in the view of either the investigator or sponsor, it results in any of the following outcomes: death, a life-threatening adverse event, or a persistent or significant incapacity or substantial disruption of the ability to conduct normal life functions. Important medical events that may not result in death, be life-threatening, or require hospitalization may be considered serious when, based upon appropriate medical judgment, they may jeopardize the participant and may require medical or surgical intervention to prevent one of the outcomes listed in this definition.

8.3.3 CLASSIFICATION OF AN ADVERSE EVENT

8.3.3.1 SEVERITY OF EVENT

For adverse events (AEs) not included in the protocol defined grading system, the following guidelines will be used to describe severity.

- **Mild** – Events require minimal or no treatment and do not interfere with the participant's daily activities.
- **Moderate** – Events result in a low level of inconvenience or concern with the therapeutic measures. Moderate events may cause some interference with functioning.
- **Severe** – Events interrupt a participant's usual daily activity and may require systemic drug therapy or other treatment. Severe events are usually potentially life-threatening or incapacitating. Of note, the term "severe" does not necessarily equate to "serious".

8.3.3.2 RELATIONSHIP TO STUDY INTERVENTION

All adverse events (AEs) must have their relationship to study intervention assessed by the medical professionals on the study team based on temporal relationship and their clinical judgment. The degree of certainty about causality will be graded using the categories below.

- **Related** – The AE is known to occur with the study intervention, there is a reasonable possibility that the study intervention caused the AE, or there is a temporal relationship between the study intervention and event. Reasonable possibility means that there is evidence to suggest a causal relationship between the study intervention and the AE.
- **Not Related** – There is not a reasonable possibility that the administration of the study intervention caused the event, there is no temporal relationship between the study intervention and event onset, or an alternate etiology has been established.

8.3.3.3 EXPECTEDNESS

The medical professionals on the study team will be responsible for determining whether an adverse event (AE) is expected or unexpected. An AE will be considered unexpected if the nature, severity, or frequency of the event is not consistent with the risk information previously described for the study intervention.

8.3.4 TIME PERIOD AND FREQUENCY FOR EVENT ASSESSMENT AND FOLLOW-UP

The occurrence of an adverse event (AE) or serious adverse event (SAE) may come to the attention of study personnel during the preparation of monthly adverse event reports or half-yearly presentations to the DSMB.

All AEs will be recorded. Information to be collected includes event description, time of onset, clinician's assessment of severity, and relationship to study. All AEs will be followed to adequate resolution.

8.3.5 ADVERSE EVENT REPORTING

All adverse events will be reported to the DSMB at the subsequent DSMB meeting.

8.3.6 SERIOUS ADVERSE EVENT REPORTING

The principal investigator will immediately report to the sponsor and DSMB any serious adverse event, whether or not considered study intervention related, and must include an assessment of whether there is a reasonable possibility that the study intervention caused the event.

8.3.7 REPORTING EVENTS TO PARTICIPANTS

Not applicable.

8.3.8 EVENTS OF SPECIAL INTEREST

Not applicable.

8.3.9 REPORTING OF PREGNANCY

Not applicable.

8.4 UNANTICIPATED PROBLEMS

8.4.1 DEFINITION OF UNANTICIPATED PROBLEMS (UP)

The Office for Human Research Protections (OHRP) considers unanticipated problems involving risks to participants or others to include, in general, any incident, experience, or outcome that meets all of the following criteria:

- Unexpected in terms of nature, severity, or frequency given (a) the research procedures that are described in the protocol-related documents, such as the Institutional Review Board (IRB)-approved research protocol and informed consent document; and (b) the characteristics of the participant population being studied;
- Related or possibly related to participation in the research (“possibly related” means there is a reasonable possibility that the incident, experience, or outcome may have been caused by the procedures involved in the research); and
- Suggests that the research places participants or others at a greater risk of harm (including physical, psychological, economic, or social harm) than was previously known or recognized.

8.4.2 UNANTICIPATED PROBLEM REPORTING

The investigators will report unanticipated problems (UPs) to the reviewing Institutional Review Board (IRB). The UP report will include the following information:

- Protocol identifying information: protocol title and number, PI’s name, and the IRB project number;
- A detailed description of the event, incident, experience, or outcome;
- An explanation of the basis for determining that the event, incident, experience, or outcome represents an UP;
- A description of any changes to the protocol or other corrective actions that have been taken or are proposed in response to the UP.

To satisfy the requirement for prompt reporting, UPs will be reported using the following timeline:

- UPs that are serious adverse events (SAEs) will be reported to the IRB within <insert timeline in accordance with policy> of the investigator becoming aware of the event.
- Any other UP will be reported to the IRB and to the DCC/study sponsor within <insert timeline in accordance with policy> of the investigator becoming aware of the problem.
- All UPs should be reported to appropriate institutional officials (as required by an institution’s written reporting procedures), the supporting agency head (or designee), and the Office for Human Research Protections (OHRP) within <insert timeline in accordance with policy> of the IRB’s receipt of the report of the problem from the investigator.]

8.4.3 REPORTING UNANTICIPATED PROBLEMS TO PARTICIPANTS

Not applicable.

9 STATISTICAL CONSIDERATIONS

9.1 STATISTICAL HYPOTHESES

The null hypotheses are that (1) $\beta_1 = 0$, (2) $\beta_2 = 0$, and (3) $\beta_1 = \beta_2$ in the hierarchical linear model

$$Y_{ipsh} = \beta_0 + \beta_1 ARM1_{sh} + \beta_2 ARM2_{sh} + \gamma_{1h} ARM1_{sh} + \gamma_{2h} ARM2_{sh} + \omega_1 X_{ipsh} + \omega_2 Z_{psh} + \omega_3 U_{sh} + \omega_4 W_h + \gamma_h + \eta_{sh} + \varphi_{psh} + \varepsilon_{ipsh}, \quad (1)$$

where i is the patient treated by surgeon p in specialty s at hospital h , $ARM1_{sh}$ and $ARM2_{sh}$ are indicator variables for whether specialty s at hospital h were assigned to intervention arm one or two respectively, X is a set of patient covariates, Z is a set of surgeon covariates, U is a set of specialty covariates, and W is a set of hospital covariates.

The alternative hypotheses are that (1) $\beta_1 \neq 0$, (2) $\beta_2 \neq 0$, and (3) $\beta_1 \neq \beta_2$.

